## IRB Minimal Risk Protocol Template

**Note: If this study establishes a human specimen repository (biobank) for research purposes, do not use this template. Use the Mayo Clinic Human Specimen Repository Protocol Template found on the IRB home page under Forms and Procedures at <http://intranet.mayo.edu/charlie/irb/>**

**First-time Use:** Use this template to describe your study for a new IRB submission.

1. Complete the questions that apply to your study.
2. Save an electronic copy of this protocol for future revisions.
3. When completing your IRBe application, you will be asked to upload this document to the protocol section.

**Modification:** To modify this document after your study has been approved:

1. Open your study in IRBe. Click on the study 'Documents' tab and select the most recent version of the protocol. Save it to your files.
2. Open the saved document and activate "Track Changes".
3. Revise the protocol template to reflect the modification points , save the template to your files
4. Create an IRBe Modification for the study and upload the revised protocol template.

## Research Question and Aims

**Aims, purpose, or objectives:** The purpose of this study is to evaluate the accuracy with which a programmable treadmill delivers controlled postural disturbances under real world use scenarios (i.e., with a subject on the treadmill belt).

**Hypothesis:** We hypothesize that the observed disturbance parameters will show acceptable agreement with the command disturbance parameters. In other words, a Bland-Altman plot 95% confidence interval of differences between input and observed characteristics will contain zero.

**Background (Include relevant experience, gaps in current knowledge, preliminary data, etc.):** Compensatory step training safely induces a fall by delivering large postural disturbances, in turn requiring subjects to arrest a fall through timely well-placed steps and reduced trunk rotation (Owings et al., *Clin Biomech.* 16:813-9, 2001; Crenshaw et al., *J Biomech.* 45:129-33, 2012). Such training has reduced falls in the laboratory (Grabiner et al., *Med Sci Sports Exerc.* 44:2410-4, 2012) and free-living environment (Rosenblatt et al., *JAGS*, 61:1629-31, 2013, Kaufman et al., *Clin Orth Related Res.* 472:3076-3084, 2014). The ability to respond to a disturbance without stepping (Pai et al., *J Biomech.* 31:1111-1118, 1998) or by taking only one step (Rogers et al., *J*

*Gerontol.* 56A:M589-M594, 2001; Hilliard et al., *Arch Phys Med Rehabil.* 89:1708-1713, 2008) is reduced for individuals who fall compared to non-fallers. These results suggest that assessments that focus on the ability to respond to external disturbances have utility in prospectively identifying fallers. Such assessments and interventions, however, must use equipment that precisely delivers postural disturbances of various magnitudes. The purpose of this study is to evaluate the accuracy with which a programmable treadmill delivers controlled postural disturbances. The new treadmill (Treadmetrix, Park City, UT) is instrumented with force sensors and has been custom programmed to deliver postural disturbances in a similar manner to treadmills previously validated under IRB 14-000939 from the same PI.

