touch the treadmill. These methods are similar to other protocols in progress or in completion (IRB 11-006984, IRB 12-002515, IRB 13-000605, IRB 14-000939, IRB 15-004618, IRB 15-005602, IRB 16-000754, IRB 16-002999, IRB 19-007775). A maximum of 50 disturbances will be delivered.

The testing session will be video recorded as a method of study quality control to help study staff determine if a fall occurred during a treadmill disturbance. If a video clip of the testing will be used for presentation purposes, the volunteer's face will be concealed to protect their privacy.

The dependent variables from this assessment are the treadmill belt displacements, belt peak velocities, treadmill force, treadmill moment, center of pressure, and initial belt accelerations.

Subjects will be allowed to rest at their request. The protocol will be video recorded for documentation purposes.

**Resources:** *Describe the available resources to conduct the research (personnel, time, facilities, mentor commitment, etc.):* The Motion Analysis Laboratory contains all equipment listed in the protocol. Three engineers are assigned to the project to run the data collection trials, process data, and disseminate the results through presentations and manuscripts.

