## Data Analysis

*Power analyses may not be appropriate if this is a feasibility or pilot study, but end-point analysis plans are always appropriate even if only exploratory. Provide all information requested below, or provide justification if not including all of the information.*

**Power Statement:** 20 subjects will each perform 50 trials (1000 data points for each treadmill). With 1000 data points, we can accurately estimate the limits of agreement to within  $+\/- 1.96 \sqrt{2 \left( \frac{3}{n} \right)}$  s or  $+\/- 0.11$  standard deviations (Bland and Altman, *Lancet*, i:307-10, 1986).

**Data Analysis Plan:** Data will be analyzed using custom software (MATLAB, Mathworks, Natick, MA). The following dependent variables will be recorded for each visit:

- Treadmill belt displacement
- Treadmill belt peak velocity
- Treadmill belt average initial acceleration
- Treadmill force
- Treadmill moment
- Center of pressure location and excursion

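### The hypothesis defines acceptable agreement as a 95% interval of differences containing zero, which puts no limit on the treadmill's error and makes a pass easier as scatter grows

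*Protocol*

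**What the plan says.** The Protocol's aim, in Research Question and Aims, is to "evaluate the accuracy with which a programmable treadmill delivers controlled postural disturbances under real world use scenarios". The Hypothesis in the same section reads "We hypothesize that the observed disturbance parameters will show acceptable agreement with the command disturbance parameters. In other words", and what follows those last words is the operational rule: "a Bland-Altman plot 95% confidence interval of differences between input and observed characteristics will contain zero". The Background gives the reason for the study: assessments and interventions of this kind "must use equipment that precisely delivers postural disturbances of various magnitudes".

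The Power Statement in Data Analysis says that "20 subjects will each perform 50 trials (1000 data points for each treadmill" and continues "With 1000 data points, we can accurately estimate the limits of agreement to within" +/- 0.11 standard deviations. The Data Analysis Plan lists the dependent variables without an acceptance limit for any of them. The Endpoints section names completion of data collection and analysis, and publication. The zero-containing interval is thus the only criterion for agreement in the document.

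**The concern.** Whether a device is accurate enough depends on how large its errors are relative to what its use can tolerate. A rule that asks only whether an interval covers zero never compares the errors with a tolerance. The interval widens as scatter grows, so imprecision helps the device cover zero. That runs against the stated aim of accuracy and against the protocol's own requirement of precise delivery.

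The wording fits two intervals:

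- **Limits of agreement** (bias +/- 1.96 SD). The reference to a Bland-Altman plot, the phrase about differences and the Power Statement all favour this reading.
- **Confidence interval of the mean difference.** Here, failing to exclude zero is taken as evidence of agreement.

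At stake is the study's stated conclusion. Applied as written, the rule can declare a treadmill with large errors acceptable and one with small errors unacceptable.

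**Working it through.** **Inputs from the Protocol.** There are 20 subjects with 50 trials each, so n = 20 x 50 = 1000 (Data Analysis, Power Statement). Study Design and Methods makes 50 a ceiling: "A maximum of 50 disturbances will be delivered". The protocol states no bias, SD, within-subject correlation or tolerance. Every bias and SD below is an illustrative assumption, in % of the commanded value.

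**The plan's own figure.** The half-width of the 95% confidence interval around one limit of agreement is 1.96 x sqrt(3/n) SD = 1.96 x sqrt(3/1000) = 0.107 SD, which rounds to the stated 0.11. The formula in the text at hand shows an extra 2, which would give 1.96 x sqrt(6/1000) = 0.152. It is probably a root index misread from the PDF and is not counted as an error. The figure is in units of an unknown SD, so it says nothing about whether the error is tolerable.

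**Reading 1: limits of agreement.** The interval b +/- 1.96 s contains zero exactly when |b| < 1.96 s.

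| Bias b | SD s | Limits | Contains zero? |
|---|---|---|---|
| 1% | 0.4% | 1 +/- 0.784 = 0.216% to 1.784% | No: fails |
| 10% | 6% | 10 +/- 11.76 = -1.76% to 21.76% | Yes: passes |
| 0 | 20% | -39.2% to 39.2% | Yes: passes |

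An unbiased treadmill passes at any scatter.

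**Reading 2: confidence interval of the mean difference.** The 50 trials within a subject may be correlated. With intraclass correlation ICC, the effective number of differences is n_eff = 1000/(1 + 49 x ICC). This gives 1000 at ICC 0, 1000/25.5 = 39.2 at ICC 0.5 and 1000/50 = 20 at ICC 1. The half-width is 1.96/sqrt(n_eff) = 0.062, 0.313 and 0.438 SD respectively.

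With r = b/s, the probability that the interval contains zero is Phi(1.96 - r sqrt(n_eff)) - Phi(-1.96 - r sqrt(n_eff)). For a bias of 1%:

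| SD | r | ICC 0 | ICC 0.5 | ICC 1 |
|---|---|---|---|---|
| 2% | 0.5 | about 0 | 0.121 | 0.391 |
| 20% | 0.05 | 0.647 | 0.939 | 0.944 |
| 40% | 0.025 | 0.876 | 0.947 | 0.949 |

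In every column the chance of passing rises with scatter. Correlation changes the size of the contrast, not its direction. At zero bias the probability is 0.95 whatever the SD.

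**Comparison with a rule that has a margin.** Suppose instead that the outer 95% confidence bounds of both limits had to lie within +/- Delta. The larger outer bound in absolute value is |b| + s x (1.96 + 1.96 x sqrt(3/n_eff)). The multiplier of s is 1.96 + 0.107 = 2.07 at n_eff = 1000 and 1.96 + 0.759 = 2.72 at n_eff = 20.

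- Bias 1%, SD 0.4%: 1 + 0.4 x 2.07 = 1.83% up to 1 + 0.4 x 2.72 = 2.09%.
- Bias 10%, SD 6%: 10 + 6 x 2.07 = 22.4% up to 10 + 6 x 2.72 = 26.3%.

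Any Delta between about 2.1% and 22.4% would therefore pass the first device and fail the second, whatever the correlation. Both verdicts under reading 1 are reversed.

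**The case against.** The strongest reply is that the damage is limited. The endpoints are completion and publication, no release or clinical decision hangs on the verdict, and the bias and limits of agreement would still be estimated and can be judged by any reader. This is true: the data and the estimation are sound. But the sentence is the study hypothesis, and nothing else in the document defines success.

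A second reply is that a SAP could supply the margin. It could, but only by departing from what the hypothesis says. The fault is a criterion that is stated and wrong, not a detail left for later.

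Third, the numerical examples are chosen to show the contrast, and nothing in the protocol suggests that a programmable treadmill scatters by 20% or 40%. That is fair. They show that misclassification is possible, not that it is likely. Under the limits-of-agreement reading a false failure needs |bias| above 1.96 SD, so that half of the problem is narrower there than under the mean reading, where a bias well above 0.062 SD (independent trials) tends to fail.

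Fourth, ICC 1 is a mathematical bound rather than a plausible case, and t on 19 degrees of freedom would be more exact there. It moves 0.39 to 0.44 and 2.72 to 2.77, which changes nothing material.

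Finally, the minimum cure is a justified tolerance against which the limits are judged. Requiring the outer confidence bounds to meet it, and using a repeated-measures calculation, go beyond that minimum. Both are defensible and cheap, but they are choices.

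**Conclusion.** The concern holds and must be fixed. The protocol equates acceptable agreement with an interval that contains zero, and neither reading of that interval bounds the error. That result is algebraic and needs no assumed value. An unbiased treadmill passes at any scatter: always under the limits-of-agreement reading, and about 95% of the time under the mean reading.

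The size of a misclassification depends on a bias and SD that the protocol does not give, so the figures above are illustrations under normal theory. The invalid part is the pass/fail conclusion on accuracy; the reported bias and limits of agreement would stand.

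**What to change.** Replace the operational sentence of the Hypothesis with wording such as: *For belt displacement, peak velocity and average initial acceleration, agreement is acceptable if the outer 95% confidence bounds of both 95% limits of agreement (observed minus command) lie within +/- Delta.*

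- The sponsor fixes Delta for each parameter before data are examined and states whether it is absolute or a percentage of command, since the disturbances vary in magnitude. Delta should be justified by the error that the intended use can tolerate, preferably not by the error an earlier device achieved.
- Compute the limits and their confidence bounds with trials nested in subjects, by between- and within-subject variance components or a bootstrap that resamples subjects, not as 1000 independent points.
- Report the mean bias with its confidence interval as an estimate, not as a test.

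The cost is one protocol sentence, one justified tolerance per belt parameter and a repeated-measures calculation. The downside for the sponsor is that the treadmill can now fail for imprecision. Whether 20 subjects suffice cannot be checked until Delta and an expected bias and SD are stated. To pass, |bias| + 2.07 SD (independent trials), rising to |bias| + 2.72 SD (fully correlated within subject), must be no more than Delta.

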## Subject Information

*Target accrual is the proposed total number of subjects to be included in this study at Mayo Clinic. A "Subject" may include medical records, images, or specimens generated at Mayo Clinic and/or received from external sources.*

Target accrual: 20 healthy adults

Subject population (children, adults, groups): Adults aged 18-45

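### The contain-zero agreement rule, if applied to differences pooled over all commanded disturbances, does not test accuracy across the range of disturbance sizes

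*Protocol*

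**What the plan says.** The Hypothesis (Protocol, Research Question and Aims) expects that "the observed disturbance parameters will show acceptable agreement with the command disturbance parameters". It then restates this as one criterion: "a Bland-Altman plot 95% confidence interval of differences between input and observed characteristics will contain zero". The criterion does not refer to the size of the commanded disturbance and gives no limit on acceptable error.

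The Background in the same section says that assessments and interventions of this kind "must use equipment that precisely delivers postural disturbances of various magnitudes".

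The Power Statement (Data Analysis) says that "20 subjects will each perform 50 trials (1000 data points for each treadmill") and continues: "With 1000 data points, we can accurately estimate the limits of agreement to within" ±0.11 standard deviations. It uses one n and one s. The Data Analysis Plan below it lists variables and adds no decision rule. Study Design and Methods adds only "A maximum of 50 disturbances will be delivered", with no list of commanded levels.

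**The concern.** A device can be right on average and wrong at both ends of its range. It can also drift steadily further from the command as the command grows. A single interval over all trials cannot separate these patterns from accurate delivery. The Protocol's wording leaves open whether the interval is the confidence interval for the mean difference or the limits of agreement, so both need checking. At stake is the study's main conclusion: the rule could be met, and the treadmill declared to agree with its commands, although the error depends on disturbance size. The pooled limits would then describe neither small nor large disturbances.

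**Working it through.** **Inputs from the Protocol.** 20 subjects × 50 trials = 1000 differences; one s; the contain-zero rule; stated precision ±0.11 SD.

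**Assumptions (the Protocol gives no values).** Five equally used command levels (200 trials each), normal errors, independent points. All errors are in units of the within-level SD.

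**The plan's own figure.** 1.96 × √(3/1000) = 0.107, which rounds to the stated 0.11. The formula in the text at hand also shows a 2 under the root. Taken literally that gives 1.96 × √(6/1000) = 0.152, but it is most likely the root index displaced in text extraction. The figure reproduces.

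**Reading A: interval for the mean.** Let bias run -0.5, -0.25, 0, 0.25, 0.5.
- Pooled mean = 0. Variance of the biases = 0.125, so pooled SD = √1.125 = 1.061.
- Pooled half-width = 1.96 × 1.061/√1000 = 0.066. Zero is contained.
- One level's half-width = 1.96/√200 = 0.139. The bias at each end is 0.5/0.139 = 3.6 times that.
- Cancellation must be close. With the pooled mean off by d and sampling SE 1/√1000, the chance of containing zero is 69% at d = 0.05, 50% at 0.066 and 14% at 0.10.

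**Reading B: limits of agreement.** Let bias be k × c for command c, with within-level SD 1. The pooled limits contain zero while k × mean(c) < 1.96 × √(1 + k² var(c)), that is, while k < 1.96/√(mean(c)² − 3.8416 var(c)). The largest level's own limits exclude zero once its bias exceeds 1.96.

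| Levels | Largest:smallest | Top-level bias beyond which pooled limits exclude zero |
|---|---|---|
| all equal | 1 | 1.96 (no effect of pooling) |
| 1, 1.25, 1.5, 1.75, 2 | 2 | 2.95 |
| 1, 1.5, 2, 2.5, 3 | 3 | 4.08 |
| 1, 2, 3, 4, 5 | 5 | 8.54 |

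Example, levels 1 to 5 with top bias 3 (k = 0.6):
- Mean = 0.6 × 3 = 1.8; SD = √(1 + 0.36 × 2) = 1.311.
- Pooled limits = 1.8 ± 1.96 × 1.311 = -0.77 to 4.37, which contain zero.
- Top level's own limits = 3 ± 1.96 = 1.04 to 4.96, which exclude it.

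**Changing SD, no bias.** If SD rises linearly from 1 to r, coverage of the pooled 95% limits at the smallest/largest level is 95.0/95.0% for r = 1, 97.3/92.3% for 1.25, 98.7/90.1% for 1.5 and 99.7/86.9% for 2. The ends swap if SD falls.

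**Precision if limits are reported by command.** At an end level the regression leverage is 1/n + 2/n = 3/n.
- Constant SD: 1.96 × √((3 + 1.96²/2)/1000) = 0.14 SD.
- SD also modelled on command: 1.96 × √(3 × (1 + 1.96²/2)/1000) = 0.18 SD.
- Separate limits per level: 1.96 × √(3/200) = 0.24 SD.

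**Repeating contain-zero at each level.** With no true error, five independent 95% intervals for the mean all contain zero with probability 0.95⁵ = 0.77. A perfectly accurate treadmill would fail about one time in four.

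**The case against.** The Protocol nowhere says that differences will be pooled over command levels. That is inferred from one interval in the Hypothesis and one n and s in the Power Statement. A statistical analysis plan, not at hand, may examine proportional bias, and its absence here is no fault. A Bland-Altman plot also displays a trend with size. These points stand, and the concern is worded conditionally because of them. But neither a plot nor an added analysis changes the stated criterion, which could still be met.

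The mean-interval case is fragile. It needs near cancellation, and error in one direction would be caught: in a simulation with assumed inputs (levels at 0.2 to 1.0 of maximum, error SD 0.02 of maximum), uniform under-delivery of 5% or 10% never left zero inside the interval for the mean. The same errors left zero inside the limits of agreement every time. Also, 3.6 half-widths measures detectability at n = 200, not practical importance; half an SD may be trivial in physical units.

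Under the limits-of-agreement reading, pooling is not the only weakness. Contain-zero passes any constant bias below 1.96 SD with no dependence on size at all, because the rule sets no bound on error. Judging across the range is therefore not enough without such a bound.

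A reader might infer that the treadmill is inaccurate at some magnitudes, that the planned analysis will certainly mislead, or that ±0.11 SD is miscalculated. The Protocol supports none of these. It has no error data and no levels, and the 0.11 reproduces.

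**Conclusion.** The point holds in conditional form. Applied to pooled differences, the stated criterion does not test accuracy across disturbance sizes under either reading of the interval. For the mean, it can be met through close cancellation. For the limits of agreement, it becomes easier to meet as proportional bias grows: with a 5:1 command range, the pooled limits still contain zero up to a top-level bias of 8.54 SD, against 1.96 for that level's own limits. These sizes rest on assumed levels, equal use of levels, normal errors and independence. The actual effect may be nil, and it is nil if bias and SD do not change with command.

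The ±0.11 SD figure is correct for what it describes: pooled limits with constant bias and SD and independent points. The 1000 points are in fact 50 repeats in each of 20 subjects, which is a separate matter and adds no weight here. This is a cheap improvement to a criterion that the Protocol itself fixes.

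**What to change.** For each belt variable that has a commanded value:

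1. Regress the difference on the commanded value with a random subject effect, and check whether the residual SD changes with command.
2. Report bias and limits of agreement as a function of command, either regression-based or as a percentage of command.
3. Base the agreement conclusion on whether those limits stay within a maximum acceptable error over the command range. The investigators should set that error before analysis; the Protocol gives no basis for naming a value here.
4. Do not base the conclusion on a pooled interval containing zero, and do not repeat contain-zero level by level.
5. State beside the ±0.11 SD that it applies to pooled limits with constant bias and SD and independent points.

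The cost is a few sentences, one regression per belt variable and agreement on the error bound, with no new subjects, trials or procedures. The downside is a little more analysis and less precise limits at the ends of the range: about ±0.14 SD with constant SD, or ±0.18 SD if SD is also modelled, under five equal levels and independence. Within-subject correlation would widen these.

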### Study Design and Methods

**Methods:** *Describe in lay terms, completely detailing the research activities that will be conducted by Mayo Clinic staff under this protocol.*

Subjects will participate for a single 2 hour visit in the Motion Analysis Laboratory. Subjects will be asked to wear comfortable athletic shoes and clothing. Subjects will give written informed consent. A study team member will ask the subject questions about their medical history to see if they qualify for the study. These questions (with required answers) are as follows:

- What is your age? (Age must be between 18 to 45 years)
- Do you have current or chronic pain in your shoulders, elbows, hips, knees, ankles, feet, neck or back? (no)
- Do you have any medical conditions or previous injuries, trauma, or surgeries that reduce your balance, mobility or strength? (no)
- Do you use an assistive device such as a cane or walker? (no)

A study team member will measure the subject's height and mass. The subject's clinic number, birth date, gender, and preferred-kicking limb will be recorded.

The protocol is as follows:

Four reflective markers will be placed bilaterally on the subject's heel and toe. Additional markers will be placed on the treadmill belts. The three-dimensional trajectories of each marker will be recorded with a motion capture system (Motion Analysis Corporation, Santa Rosa, CA). Marker trajectories will be used to determine foot placement. While subjects are on the instrumented treadmill, force sensors in the treadmill will record ground reaction forces.

Subjects will walk on a treadmill for a period of up to 15 minutes. The walking speed will not be greater than 3.0 m/s (Diedrich et al., *Journal of Experimental Psychology*, 21:183-202, 1995). The purpose of this walking trial is to provide a period of warming up and familiarization with the treadmill.

The subjects will respond to external disturbances delivered by treadmill which has been programmed to provide the same disturbances as a commercially available, computer-controlled treadmill that is used clinically (CPT Codes: 97750, 97110, 97112, and 97116) for balance assessments and training (ActiveStep, Simbex, Lebanon, NH, <http://activestep.simbex.com/>). Before disturbances are delivered, subjects will be securely harnessed to an overhead rail so that the subject's knees and hands cannot

touch the treadmill. These methods are similar to other protocols in progress or in completion (IRB 11-006984, IRB 12-002515, IRB 13-000605, IRB 14-000939, IRB 15-004618, IRB 15-005602, IRB 16-000754, IRB 16-002999, IRB 19-007775). A maximum of 50 disturbances will be delivered.

The testing session will be video recorded as a method of study quality control to help study staff determine if a fall occurred during a treadmill disturbance. If a video clip of the testing will be used for presentation purposes, the volunteer's face will be concealed to protect their privacy.

The dependent variables from this assessment are the treadmill belt displacements, belt peak velocities, treadmill force, treadmill moment, center of pressure, and initial belt accelerations.

Subjects will be allowed to rest at their request. The protocol will be video recorded for documentation purposes.

**Resources:** *Describe the available resources to conduct the research (personnel, time, facilities, mentor commitment, etc.):* The Motion Analysis Laboratory contains all equipment listed in the protocol. Three engineers are assigned to the project to run the data collection trials, process data, and disseminate the results through presentations and manuscripts.

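### Do treadmill force, moment and center of pressure need a reference value in a study of command-versus-observed agreement?

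*Protocol*

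**What the plan says.** The aim, in Research Question and Aims, is to "evaluate the accuracy with which a programmable treadmill delivers controlled postural disturbances under real world use scenarios". The hypothesis there is that "observed disturbance parameters will show acceptable agreement with the command disturbance parameters", made operational as the requirement that "a Bland-Altman plot 95% confidence interval of differences between input and observed characteristics will contain zero".

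Study Design and Methods gives one undivided list of dependent variables: belt displacement and peak velocity, followed by "treadmill force, treadmill moment, center of pressure, and initial belt accelerations". The Data Analysis Plan repeats the list with small changes of wording (center of pressure becomes its location and excursion). It says that these quantities are recorded and gives no comparator and no separate role for any of them.

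On instruments, Study Design and Methods states that "force sensors in the treadmill will record ground reaction forces". Reflective markers go on the heels and toes and on the belts, and their stated use is to determine foot placement. Each subject's "height and mass" are measured. No second force instrument, known load or calibration step is described.

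The Power Statement is expressed as the precision of limits of agreement: 20 subjects with 50 trials each, and 0.11 standard deviations either way.

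**The concern.** A Bland-Altman analysis needs two values for each observation. Belt motion has them: what the controller was told to do and what the belt did. Ground reaction force, moment and center of pressure are not commanded. They result from the subject's mass and stepping response, and the device under test is their only described source. For these three there is no difference to plot and no limit of agreement to estimate, yet they share one list with the belt variables.

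If the study meant to certify all six, half of that claim would have no support, and a miscalibrated force sensor could pass unnoticed. The point seems sharper because the treadmill is new, is described as instrumented with force sensors, and is introduced beside treadmills that were validated earlier. A partial reference also seems to be at hand, since body mass is measured and the feet carry markers.

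**Working it through.** **1. The plan's own precision figure.** Inputs from the Power Statement: 20 subjects and 50 trials, so n = 20 × 50 = 1000. The usual approximation for the standard error of a limit of agreement is s√(3/n), where s is the standard deviation of the differences. The half-width is then

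1.96 × √(3/1000) = 1.96 × 0.0548 = 0.107,

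which rounds to the stated 0.11 s. The variant 1.96 × √(1/n + 1.96²/(2(n − 1))) gives 0.106, also 0.11. The formula as it appears in the text carries an extra factor 2 under the root, which would give 1.96 × √(6/1000) = 0.152. The stated 0.11 agrees with the form without it, so the 2 may be a root index misread from the PDF.

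The figure is in units of s and has meaning only where a difference exists. It takes the 1000 data points at the plan's own count.

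**2. Which variables can form a difference.**

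| Variable | Commanded value | Observed value | Difference possible |
|---|---|---|---|
| Belt displacement | yes | belt motion | yes |
| Belt peak velocity | yes | belt motion | yes |
| Initial belt acceleration | yes | belt motion | yes |
| Force | none | treadmill sensors | no |
| Moment | none | treadmill sensors | no |
| Center of pressure | none | treadmill sensors | no |

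The protocol does not itemize the commanded parameters. The first three rows assume that a programmed belt disturbance is specified by its displacement, velocity and acceleration. On that reading 3 of 6 variables have a pair and 3 do not, so the factual part of the concern is correct.

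**3. Whether the plan claims anything about the other three.** Three statements settle this.

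- The aim concerns the accuracy of delivered disturbances. Force under the feet is a response to a disturbance, not a property of what was commanded.
- The hypothesis compares observed with commanded disturbance parameters, and its criterion uses "differences between input and observed characteristics". A quantity with no input falls outside this by definition.
- The Data Analysis Plan says of the six variables only that they are recorded.

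No sentence states that force, moment or center of pressure will be tested for accuracy. The agreement hypothesis is already confined to the variables for which it can be evaluated.

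**4. What an added force check would need.** Mean vertical force in quiet standing, or over whole strides, should equal mass × g. For an illustrative 70 kg subject that is 70 × 9.81 = 686.7 N, and an illustrative 5% error would be 34.3 N, or 3.5 kg. Such an error would be visible in suitable data. Against the procedures in Study Design and Methods:

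- no quiet-standing trial is described;
- the warm-up walk is on a treadmill that is not identified as the instrumented one;
- subjects are harnessed before disturbances and no measurement of harness load is described, so unloaded frames cannot be confirmed directly;
- heel and toe markers show where the foot is and so only bound the center of pressure;
- body weight checks mean vertical force only, and leaves moments, horizontal force and force during a disturbance untested.

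**The case for a change.** The strongest case for a change is that a missing reference is a matter of data collection, not of analysis. Each subject attends once. If no suitable force data without harness load are captured then, a later analysis plan cannot create them. Listing six dependent variables together, for a treadmill introduced as force-instrumented, also invites a reader to treat all six as validated, and a single sentence would prevent that.

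Part of this stands. The lists do not separate the belt variables from the force-based ones, and a sentence calling the latter descriptive would be tidy. It is also true that an analysis plan could not supply a reference afterwards. That second point has force only if an accuracy claim for these variables was intended, and none is stated. Dependent variable is an ordinary label for anything measured as an outcome. Force and center of pressure can serve to describe the subject's response or the load on the belt, which suits an aim of testing with a person on the treadmill. How such measures are summarized is commonly left to an analysis plan, which is not at hand here.

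**Conclusion.** The observation is correct but calls for no change. Three of the six variables have no comparator, and neither the hypothesis nor the precision of 0.11 standard deviations extends to them. The protocol's wording already limits the agreement test to parameters with a commanded value, so an analyst following it would apply Bland-Altman to the three belt variables and report the others without an accuracy claim. The result for the study's main question is the same with or without a label on the remaining three.

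Comparing vertical force with body weight, or center of pressure with foot markers, would answer a question that the study does not ask. It would probably need an added recording or assurances about harness load, and would still leave moments and force during disturbances unchecked.

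This conclusion rests on two assumptions: that the commanded parameters are belt displacement, peak velocity and initial acceleration, and that no claim of validated force measurement is intended, since none is written. If such a claim were made in a report, it would have no support from this design, and the concern would then apply in full.
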